12.0 Potential Benefits to Subjects and Others

12.1 Potential Benefits to Subjects

The potential benefits to subject may be a decrease in pain and narcotic use.

12.2 Potential Benefits to Others

Endometriosis is a devastating disease that impacts nearly 1:10 women in the reproductive years or their life. The pathophysiology of endometriosis is not completely understood, however, there is strong evidence that inflammation plays a major role in the symptoms associate with endometriosis. Current strategies for the management of endometriosis-associated pain often leave women seeking additional relief in the form of opioid-based treatments. In light of the current opioid epidemic it is important that we continue seek non-opioid based therapies that can provide symptomatic relief while we continue to try and better understand this debilitating disease. LDN has gained some popularity as an off-label

treatment for inflammatory conditions such as multiple sclerosis, Crohn's disease and fibromyalgia, which can potentially be utilized in endometriosis as well.

13.0 Sharing Results with Subjects

There is no information for the patient to receive as no diagnostics will be done.

14.0 Subject Stipend (Compensation) and/or Travel Reimbursements

Subject will receive \$25 at the completion of the screening visit and \$100 additional at the completion of the study for a total of \$125. We will not be providing travel reimbursement as part of this study protocol.

15.0 Economic Burden to Subjects

15.1 Costs

All tests and procedures required for participation in the study will be paid for by the sponsor. There are no additional costs to subjects participating in the research. Analgesics taken during the study will be paid for by the subject and/or her insurance.

15.2 Compensation for research-related injury

It is the policy of the institution to provide neither financial compensation nor free medical treatment for research-related injury. In the event of injury resulting from this research, medical treatment is available but will be provided at the usual charge. Costs for the treatment of research-related injuries will be charged to subjects or their insurance carriers.

16.0 Resources Available

16.1 Facilities and locations

Locations for study visits may include the Penn State Women's Health Clinic at Hope Drive and the Clinical Research Center at the Penn State Hershey Medical Center.

16.2 Feasibility of recruiting the required number of subjects

The PI sees approximately 10 patients each week with endometriosis; approximately 30-40 are seen total within the Minimally Invasive GYN Surgery practice.

16.3 PI Time devoted to conducting the research

The PI has dedicated research time and is available to see study patients 2-3 days/week and the co-Investigator on the study asback up.

16.4 Availability of medical or psychological resources

Resources will be made available at the Penn State Hershey Medical Center, if warranted.

16.5 Process for informing Study Team

The PI, study coordinator(s) and other study team delegates will complete required study specific sponsor training throughout the conduct of the trial. OBGYN Research study team meeting occur on a

weekly basis to inform all members of the study status, responsibilities and trainings can take place. Ongoing communication via email and telephone will also take place.

17.0 Other Approvals

17.1 Other Approvals from External Entities

Not applicable

17.2 Internal PSU Committee Approvals

Check all that apply:

Anatomic Pathology – Hershey only – Research involves the collection of tissues or use of pathologic specimens. Upload a copy of HRP-902 - Human Tissue For Research Form on the "Supporting Documents" page in CATS IRB. This form is available in the CATS IRB Library.

Animal Care and Use – All campuses – Human research involves animals and humans or the use of human tissues in animals

Biosafety – All campuses – Research involves biohazardous materials (human biological specimens in a PSU research lab, biological toxins, carcinogens, infectious agents, recombinant viruses or DNA or gene therapy).

Clinical Laboratories – Hershey only – Collection, processing and/or storage of extra tubes of body fluid specimens for research purposes by the Clinical Laboratories; and/or use of body fluids that had been collected for clinical purposes, but are no longer needed for clinical use. Upload a copy of HRP-901 - Human Body Fluids for Research Form on the "Supporting Documents" page in CATS IRB. This form is available in the CATS IRB Library.

Clinical Research Center (CRC) Advisory Committee– All campuses – Research involves the use of CRC services in any way.

Conflict of Interest Review – All campuses – Research has one or more of study team members indicated as having a financial interest.

Radiation Safety – Hershey only – Research involves research-related radiation procedures. All research involving radiation procedures (standard of care and/or research-related) must upload a copy of HRP-903 - Radiation Review Form on the "Supporting Documents" page in CATS IRB. This form is available in the CATS IRB Library.

IND/IDE Audit – All campuses – Research in which the PSU researcher holds the IND or IDE or intends to hold the IND or IDE.

Scientific Review – Hershey only – All investigator-written research studies requiring review by the convened IRB must provide documentation of scientific review with the IRB submission. The scientific review requirement may be fulfilled by one of the following: (1) external peer-review process; (2) department/institute scientific review committee; or (3) scientific review by the Clinical Research Center Advisory committee. NOTE: Review by the Penn State Hershey Cancer Institute Scientific Review Committee is required if the study involves cancer prevention studies or cancer patients, records and/or tissues. For more information about this requirement see the IRB website at: http://www.pennstatehershey.org/web/irb/home/resources/investigator

18.0 Multi-Site Research

18.1 Communication Plans

Not applicable

18.2 Data Submission and Security Plan

Not applicable

18.3 Subject Enrollment

Not applicable

18.4 Reporting of Adverse Events and New Information

Not applicable

18.5 Audit and Monitoring Plans

Not applicable

19.0 Adverse Event Reporting

19.1 Adverse Event Definitions

For drug studies, incorporate the following definitions into the below responses, as written:	
Adverse event	Any untoward medical occurrence associated with the use of the drug in
	humans, whether or not considered drug related
Adverse reaction	Any adverse event caused by a drug
Suspected adverse	Any adverse event for which there is a reasonable possibility that the drug
reaction	caused the adverse event. Suspected adverse reaction implies a lesser degree
	of certainty about causality than "adverse reaction".
	Reasonable possibility. For the purpose of IND safety reporting,
	"reasonable possibility" means there is evidence to suggest a causal
	relationship between the drug and the adverse event.
Serious adverse	Serious adverse event or Serious suspected adverse reaction: An adverse event
event or Serious	or suspected adverse reaction that in the view of either the investigator or
suspected adverse	sponsor, it results in any of the following outcomes: Death, a life-threatening
reaction	adverse event, inpatient hospitalization or prolongation of existing
	hospitalization, a persistent or significant incapacity or substantial disruption
	of the ability to conduct normal life functions, or a congenital anomaly/birth
	defect. Important medical events that may not result in death, be life-
	threatening, or require hospitalization may be considered serious when, based
	upon appropriate medical judgment, they may jeopardize the patient or
	subject and may require medical or surgical intervention to prevent one of the
	outcomes listed in this definition.
Life-threatening	An adverse event or suspected adverse reaction is considered "life-
adverse event or	threatening" if, in the view of either the Investigator (i.e., the study site
life-threatening	principal investigator) or Sponsor, its occurrence places the patient or research
suspected adverse	subject at immediate risk of death. It does not include an adverse event or
reaction	suspected adverse reaction that had it occurred in a more severe form, might

	have caused death.
Unexpected	An adverse event or suspected adverse reaction is considered "unexpected" if
adverse event or	it is not listed in the investigator brochure, general investigational plan, clinical
Unexpected	protocol, or elsewhere in the current IND application; or is not listed at the
suspected adverse	specificity or severity that has been previously observed and/or specified.
reaction.	

19.2 Recording of Adverse Events

Research subjects will be routinely questioned about adverse events at study visits or survey completion days. All adverse events (serious or non-serious) and abnormal test findings observed or reported to study team believed to be associated with the study drug will be followed until the event (or its sequelae) or the abnormal test finding resolves or stabilizes at a level acceptable to the investigator. An abnormal test finding will be classified as an adverse event if one or more of the following criteria are met:

- Test finding is accompanied by clinical symptoms
- Test finding necessitates additional diagnostic evaluation or medical/surgical intervention; including significant additional concomitant drug treatment or other therapy.

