The study will include a 12-week intervention period during which subjects will be asked to record daily electronic VAS scores, report daily analgesic use (NSAIDs and opioids) and complete surveys every 4 weeks. VAS scores will be reported daily. Patient Global Impression of Change (PGIC), Patient Global Assessments (for pain, dysmenorrhea, nonmenstrual pelvic pain and function) (PGAs) and Endometriosis Health Profile-30 (EHP 30) surveys will be completed at 4-week intervals during the intervention (0, 4, 8, and 12 weeks). Subjects will be asked to complete a brief telephone interview visit at 16 weeks to complete final quality of life surveys (EHP 30, PGAs and PGIC).

Subjects will be screened for side effects and asked to record pain medication use throughout the duration of the study. Subjects will be dispensed a 4-week supply of medications from the Investigational Pharmacy. They will be required to bring medication bottles to each visit for counting and drug accountability. Any remaining capsules will be returned to the pharmacy. All study subjects and investigators will remain blinded to the study group until the completion of the study. In the event subjects cannot attend study visits in-person due to extenuating circumstances (e.g. related to COVID-19 pandemic), remote visits can be completed via telephone for which questionnaires will be sent via REDcap and IDS will ship of study drug. Drug accountability and monitoring for side effects can also be done via telephone.

Procedure	Pre- screen	Screening Visit (beginning of Run-in week)	Visit 1 Enrollment – Randomization (Day 1)	Visit 2* 4-weeks (Day 28- 30)	Visit 3* 8-weeks (Day 56- 58)	Visit 4* 12-weeks (Day 84- 86)	Visit 5 16-weeks Phone f/u (Day 114- 121
Screening Criteria	Х						
Informed Consent		X					
WERF Questionnaire		Х					
Physical		Х					
Past Medical History		Х					
EHP-30		Х	Х	Х	Х	Х	Х
PGIC				X	X	X	Х
PGAs		Х	Х	Х	X	Х	Х
Study Drug Dispensed & Compliance		X (Only Norethindrone Acetate given, if needed)	Х	Х	Х	Х	
Daily Pain, Analgesic and Study Medication Assessment		X (6-7 days)	X (Daily)	X (Daily)	X (Daily)	X (Daily)	X (Daily)
Screening/Assessment of Adverse Events		X	Х	X	X	X	Х

Visit Table Summary of Study Procedures

(*) - these asterisked visits can be done remotely via telephone, if warranted due to extenuating circumstances.

7.2.1 Screening visit:

Screening Visit 1:

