7.4.2 Treatment Regimen

Arm A: *Placebo:* In Arm A, the participant will be placed on the daily placebo and standard endometriosis treatment (norethindrone acetate 5 to 15mg daily dose) medication. All medications will be taken orally. Pill counts (or case packet counts) will be monitored at each in patient study visit. Norethindrone will be taken for up to 14 weeks during the study period and the study drug will be taken for up to 12 weeks during the study period.

Arm B: Low dose naltrexone: In Arm B, the participant will be placed on daily low dose naltrexone (4.5 mg daily) and standard endometriosis treatment (norethindrone acetate 5 to 15mg daily dose). All medications will be taken orally. Pill counts (or case packet counts) will be monitored at each in patient study visit. Norethindrone will be taken for up to 14 weeks during the study period and the study drug will be taken for up to 12 weeks during the study period.

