11.0 Risks

Risks of Norethindrone: Serious adverse reactions with the use of norethindrone are serious cardiovascular events and stroke, vascular events, and liver disease. Adverse reactions commonly reported by norethindrone users are: Irregular uterine bleeding, nausea, breast tenderness, and headache

Risks of Low Dose naltrexone: Adverse reactions to low dose naltrexone can include hepatotoxicity, depression and suicidality, allergic reactions, eosinophilic pneumonia, muscle cramps, dizziness or syncope, somnolence or sedation, decreased appetite, and insomnia. Everyone taking part in the study will be watched carefully for side effects; however, doctors do not know all the discomforts and risks that may happen. With all drugs there is the possibility of complications and side effects that are not known at this time. These may be mild or serious, and in some cases may be very serious, long-lasting, or may never go away. There is also a risk of death.

If you experience any side effect (or other health issues) during this study, let your study doctor know immediately. If you are not honest about your side effects, you may harm yourself by staying in this study. If you do not understand what any of these side effects mean, please ask the study doctor or study staff to explain the words to you.

Common side effects of naltrexone at higher doses include:

- Nausea, vomiting, diarrhea or constipation
- Stomach pain or cramping
- Loss of appetite
- Headache
- Dizziness
- Nervousness, irritability, or anxiety
- Tearfulness
- Increased or decreased energy

This study plans on using low dose naltrexone at a much lower dose than typically available. Multiple studies have used similar doses of naltrexone (3 - 4.5 mg) in both adult and children with no significant adverse reactions. There is no evidence reported of interactions of low dose naltrexone with other medications. The most commonly reported side effects in studies using low dose naltrexone include:

- Difficulty falling and/or staying asleep (insomnia)
- Vivid dreams
- Headaches.

Though it is an uncommon event, there is a risk of unexpected allergic reaction to the study drug which may include hives, rash, swelling or difficulty breathing. If one of the mentioned symptoms appears, stop taking your study drug(s) and seek immediate medical help.

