19.3 Causality and Severity Assessments

The investigator will promptly review documented adverse events and abnormal test findings to determine 1) if the abnormal test finding should be classified as an adverse event; 2) if there is a reasonable possibility that the adverse event was caused by the study drug(s) or device(s); and 3) if the adverse event meets the criteria for a serious adverse event.

If the investigator's final determination of causality is "unknown and of questionable relationship to the study drug(s) or device(s)", the adverse event will be classified as associated with the use of the study drug(s) or device(s) for reporting purposes. If the investigator's final determination of causality is "unknown but not related to the study drug(s) or device(s)", this determination and the rationale for the determination will be documented in the respective subject's case history.

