19.4 Reporting of Adverse Reactions and Unanticipated Problems to the FDA

19.4.1 Written IND/IDE Safety Reports

The Sponsor-Investigator will submit a written IND Safety Report (i.e., completed FDA Form 3500A) to the responsible new drug review division of the FDA for any observed or volunteered adverse event that is determined to be a serious and unexpected, suspected adverse reaction. Each IND Safety Report will be prominently labeled, "IND Safety Report", and a copy will be provided to all participating investigators (if applicable) and sub-investigators.

Written IND Safety Reports will be submitted to the FDA as soon as possible and, in no event, later than 15 calendar days following the Sponsor-Investigator's receipt of the respective adverse event information and determination that it meets the respective criteria for reporting.

For each written IND Safety Report, the Sponsor-Investigator will identify all previously submitted IND Safety Reports that addressed a similar suspected adverse reaction experience and will provide an analysis of the significance of newly reported, suspected adverse reaction in light of the previous, similar report(s) or any other relevant information.

Relevant follow-up information to an IND Safety Report will be submitted to the applicable review division of the FDA as soon as the information is available and will be identified as such (i.e., "Follow-up IND Safety Report").

If the results of the Sponsor-Investigator's follow-up investigation show that an adverse event that was initially determined to not require a written IND Safety Report does, in fact, meet the requirements for reporting; the Sponsor-Investigator will submit a written IND Safety Report as soon as possible, but in no event later than 15 calendar days, after the determination was made.

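### Section 19.2 ties follow-up to resolution, even for serious adverse events, to a belief that an undefined study drug caused them; no section commits to following a serious event firmly judged unrelated to its outcome

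*Combined protocol and SAP*

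**What the plan says.** Section 19.2 opens with a collection rule that has no causality filter: "Research subjects will be routinely questioned about adverse events at study visits or survey completion days". The visit table in 7.1 agrees, with the row "Screening/Assessment of Adverse Events" marked from the screening visit through the week-16 telephone visit.

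The next sentence of 19.2 sets the rule for following events to resolution or to an acceptable stable level. Its subject is "All adverse events (serious or non-serious) and abnormal test findings observed or reported to study team believed to be associated with the study drug", and the qualifier runs straight into the commitment: "believed to be associated with the study drug will be followed until the event (or its sequelae".

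Section 19.3 gives two outcomes where cause is uncertain. If the relationship is unknown and questionable, the event counts as drug-associated for reporting. If it is "unknown but not related to the study drug(s) or device(s", only the judgement and its reasons have to be recorded in the case history.

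Section 19.4.1 allows for a change of mind. A follow-up investigation may show that "an adverse event that was initially determined to not require a written IND Safety Report does, in fact, meet the requirements for reporting", and a report is then due within 15 calendar days of that determination.

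On terms, 7.4.2 separates the two agents: "Norethindrone will be taken for up to 14 weeks during the study period and the study drug will be taken" for up to 12 weeks. Section 11.0 lists serious harms of the hormone: "Serious adverse reactions with the use of norethindrone are serious cardiovascular events and stroke, vascular events, and liver disease". It lists hepatotoxicity for naltrexone as well.

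**The concern.** Follow-up supplies the course, outcome and sequelae of an event, and these are part of the evidence on which its cause is judged. A rule that follows only events already believed to be drug-related lets the first judgement decide whether the evidence that could overturn it is gathered. For non-serious events that is an ordinary economy. For serious events it costs more: if the first attribution is wrong, the information needed to recognise a drug reaction and report it may never be obtained.

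First attribution is difficult here. The investigator is blinded, every woman takes norethindrone, half also take naltrexone, and section 11.0 lists liver harm for both agents. The word *believed* adds to the difficulty. Section 10.2 grades events as possibly related or not, and 19.3 asks about a reasonable possibility. Section 19.2 uses a third, undefined threshold that can be read as a higher bar.

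**Working it through.** The plan gives no figure to reproduce. The check compares sections and ends with a simple bound on size.

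**Step 1. Does another section cover a serious event firmly judged unrelated?**

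| Section | What it provides | Commits to obtaining the outcome? |
|---|---|---|
| 7.1, visit table | Adverse events assessed at each visit to the week-16 call | Only as far as questioning reveals it; nothing after the last contact |
| 10.2 | Unknown cause is attributed to study participation | No; does not reach an event firmly judged unrelated |
| 10.5 | Principal investigator told at once of all serious events | No; notifies occurrence only |
| 19.3 | Unknown and questionable cause treated as associated, for reporting | No; does not reach a firm negative judgement |
| 19.7 | Six-monthly summary of all adverse events; team meets after a major serious event | No; review of what is already held |
| 20.1.1 | Independent monitoring against the protocol | No; the protocol does not require this follow-up |

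None closes the gap. What remains is a serious event, firmly judged unrelated, that is still open at last contact.

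**Step 2. What happens to the later upgrade in 19.4.1?** A written report requires an event to be serious, unexpected and a suspected reaction. An event can first miss this trigger in three ways:

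- Drug-associated but at first not serious: followed under 19.2, so the upgrade can work.
- Drug-associated but at first thought expected: followed under 19.2, so the upgrade can work.
- Firmly judged unrelated: no commitment to follow to outcome. The upgrade then relies on routine questioning to week 16, the serious-event notification and the periodic review.

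Only the third route is weakened.

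**Step 3. Does *study drug* in 19.2 include norethindrone?**

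- Suggesting no: 7.4.2 contrasts the two; 7.2.2 to 7.2.4 list norethindrone apart from the study medication; 7.2.5 offers continued norethindrone although the study drug has ended.
- Suggesting yes: 7.1 calls extra norethindrone shipments study drug; the study-drug row of the visit table includes norethindrone at screening; 7.4.5 and 7.4.6.1 list it under test-article headings.
- Section 19.2 uses the singular, while 19.3 uses a form that allows the plural. Neither defines the term.

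The documents do not settle the question.

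**Step 4. Size.** The documents state no rate of serious events. Assume 2% to 4% of the 160 randomised women (8.1, 8.2):

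- 0.02 × 160 = 3.2
- 0.04 × 160 = 6.4

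That is about 3 to 6 women with any serious event. The affected group is the subset firmly judged unrelated and unresolved at last contact. It cannot be larger than this and could be zero.

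**The case against.** The best defence is that the plan already does a good deal. Questioning about adverse events and notification of serious ones do not depend on cause. Uncertain cause defaults to drug-associated (19.3) or to study participation (10.2), so the doubtful cases are largely caught. Section 19.4.1 has its own follow-up investigation, which is not tied to 19.2. All of this stands, and it narrows the gap to the residual case in Step 1.

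Grammatically, the qualifier in 19.2 could also attach to test findings alone, in which case all adverse events would be followed. That reading is possible but less natural, and a safety rule open to both readings needs the same edit.

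A reader might infer more than the documents support:

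- *That unrelated serious events are simply not followed.* They are asked about until week 16; what is missing is a commitment to reach the outcome.
- *That 19.4.1 cannot work.* Two of its three routes are unaffected.
- *That events put down to norethindrone are excluded.* Usage is mixed; the defect is an undefined term.
- *That the 19.2 belief is fixed before the 19.3 determination.* No section says so, and 19.3 asks for prompt review.
- *That a comparison of serious harms between arms would be distorted.* Section 8.3 plans no such comparison.
- *That 3 to 6 women would go unfollowed.* That figure counts all assumed serious events, not those affected.

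**Conclusion.** The point holds in limited form. On its natural reading, 19.2 makes follow-up to resolution or stabilisation conditional on believed association with the study drug, for serious events as for others. Nothing elsewhere commits the trial to following to outcome a serious event firmly judged unrelated. Reassessment under 19.4.1 is weakened for that one class of event. Whether an event attributed to norethindrone falls under the rule is unclear.

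The number affected cannot be derived from the documents. The upper bound of about 3 to 6 of 160 rests wholly on the assumed 2% to 4% rate, and the true number is probably smaller. The conclusion concerns women still in the study. The primary analysis and the sample size are untouched. The case for acting is that a stated safety rule can be made complete at very little cost.

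**What to change.** Amend the wording as follows:

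1. In 19.2, follow every serious adverse event until it resolves or stabilises, whatever the judgement of cause.
2. In 19.2, keep a relatedness criterion for non-serious events, but replace belief with the reasonable-possibility standard already used in 19.3.
3. In 19.2 and 19.3, write *LDN/placebo or norethindrone acetate* in place of *study drug*.

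When making the change, reconcile 19.2 with 3.3.2, which plans no safety follow-up and no further data collection for withdrawn women. The two sections already conflict for drug-associated events.

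The cost is a short amendment and follow-up calls or record checks for a handful of women, at most about 3 to 6 on the assumed rate. No visits, tests or staff are added. Section 19.2 already implies contact beyond the week-16 call for drug-associated events still open then, so no new kind of procedure is needed.
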